8.6.2 Definition of Serious Adverse Events

An AE that meets one or more of the following criteria/outcomes is classified as serious (term definitions follow):

- Death
- Is deemed life-threatening
- Results in inpatient hospitalization or prolongation of an existing hospitalization
- Results in persistent or significant disability/incapacity or substantial disruption of the ability to conduct normal life functions,
- Results in a congenital anomaly/birth defect
- Important medical event

Term definitions:

Life-threatening – Any AE that places the subject at immediate risk of death from the event as it occurred. A life-threatening event does not include an event that might have

caused death had it occurred in a more severe form but that did not create an immediate risk of death as it actually occurred.

Hospitalization – Hospitalization is defined as an overnight admission with observation of a minimum of 24 hours. A hospitalization planned before the start of the study for a preexisting condition that has not worsened does not constitute an SAE (e.g. elective hospitalization for a total knee replacement due to a preexisting condition of osteoarthritis of the knee that has not worsened during the course of the study).

Disability – Defined as a substantial disruption in a person's ability to conduct normal life functions.

Congenital Anomaly/birth defect: Congenital anomaly/birth defect in offspring, or led to fetal distress, or fetal death

Important Medical Event – is an event that may not result in death, be life-threatening, or require hospitalization but may be considered serious when, based upon appropriate medical judgment of the study physicians, the event may jeopardize the subject and may require medical or surgical intervention to prevent one of the outcomes listed in this definition. Examples of such medical events include suicidality, psychosis, behavioral upset, or emergent medical condition requiring emergency hospitalization or intervention.

8.6.3 Classification of an Adverse Event

8.6.3.1 Severity of Event

For AEs not included in the protocol defined grading system, the following guidelines will be used to describe severity:

- **Mild** – Events require minimal or no treatment and do not interfere with the subject's daily activities or safety.
- **Moderate** – Events result in a low level of inconvenience or concern with the therapeutic measures. Moderate events may cause some interference with functioning or safety.
- **Severe** – Events interrupt a subject's usual daily activity and may require active medical treatment or intervention to ameliorate. Severe events are usually potentially life-threatening or incapacitating. Of note, the term "severe" does not necessarily equate to "serious".

8.6.3.2 Device related AEs

Device-related adverse events are events directly attributable to the device itself.

- **Adverse Device Effect (ADE):** Non-serious adverse event related to the use of an investigational medical device

- Serious Adverse Device Effect (SADE): Adverse device effect that has resulted in any of the consequences characteristic of a serious adverse event.

8.6.3.3 Serious Unanticipated Adverse Device Effect

Serious Unanticipated Adverse Device Effects (SUADEs) are any serious adverse effect on health or safety or any life-threatening problem or death caused by, or associated with, a device, if that effect, problem, or death was not previously identified in nature, severity, or degree of incidence in the investigational plan.

8.6.3.4 Relationship to Study Intervention

All AEs must have their relationship to study intervention assessed by a clinician who examines and evaluates the subject based on temporal relationship and his/her clinical judgment. The degree of certainty about causality will be graded using the categories below. In a clinical study, the study treatment must always be suspect.

- **Reasonable Possibility** – A clinical event, including an abnormal clinical test result, whose temporal relationship to study treatment makes a causal relationship possible. (There is reasonable evidence to suggest a partial or direct causal relationship e.g., the event occurred within a reasonable time after administration of the study treatment). Other factors may have contributed to the event (e.g., the participant's clinical condition, other concomitant events).
- **No Reasonable Possibility** – A clinical event, including an abnormal clinical test result, whose temporal relationship to study treatment makes a causal relationship improbable (e.g., the event did not occur within a reasonable time after administration of the study treatment) and in which other therapies or underlying disease provides more plausible explanations (e.g., the participant's clinical condition, other concomitant treatments).

8.6.3.5 Anticipated AEs:

The following are anticipated AEs that one or more scientific publications have previously identified as possibly related to GDH or MR therapies:

- Headache
- Drowsiness
- Fatigue
- GI discomfort
- Muscle tightness
- Muscle soreness

The Sponsor will be responsible for determining whether an AE is device-related or not.

8.6.3.6 Device malfunction

Device malfunction denotes a failure of one or more of the components of digital app that could potentially result in lack of patient access to the digital app, inconvenience. The manufacturer must confirm device failure.

8.6.4 Time Period and Frequency for Event Assessment and Follow-Up

The occurrence of an AE or SAE may come to the attention of study personnel during study visits and interviews of a study subject presenting for medical care, or upon review by a study monitor.

All AEs including not meeting the criteria for SAEs will be captured on the appropriate eCRF. Information to be collected includes event description, date of onset, clinician's assessment of severity, relationship to study product (assessed only by those with the training and authority to make a diagnosis), and date of resolution/stabilization of the event. All AEs occurring while on study must be documented appropriately regardless of relationship. All AEs will be followed to adequate resolution.

Any medical condition that is present at the time that the subject is screened will be considered as baseline and not reported as an AE. However, if the study subject's condition deteriorates at any time during the study, it will be recorded as an AE.

Changes in the severity of an AE will be documented to allow an assessment of the duration of the event at each level of severity to be performed. AEs characterized as intermittent require documentation of onset and duration of each episode.

The study team will record all events with start dates occurring any time after informed consent is obtained through the end of Phase 4 (LTE) or until the end of study participation.

Events will be followed for outcome information until resolution or stabilization.

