	
being evaluated, and at the same time the metaMe staff and investigators will not have knowledge of group assignments (see Section 7.2.1). Subjects will complete treatment, per their group assignment and all subsequent data collection will be done without human intervention via the Curebase platform.
 
The Phase 2 treatment period will initiate within 7 days of the onboarding call. Phase 2 will be initiated with the first treatment session followed by 6 additional treatment sessions occurring every 2 weeks for a total of 7 sessions over 12 weeks. Subjects will receive prompts to complete a short practice sessions on the 5th, 8th, and 11th day between treatments. Practice sessions are recommended but not required.
 
Phase 3 begins immediately after completion of Phase 2 treatment period. Subjects will provide 4 weeks of post-treatment symptom data via the ePRO and the Curebase platform. Symptoms reported in this run-out period will be used to determine the primary outcome and responder definition and secondary outcomes.
 
Phase 4 begins immediately after completion of Phase 3. Subjects will complete two post-treatment assessment periods and provide daily symptom assessments and additional instances of outcomes surveys via the ePRO and the Curebase platform. The LTE 4-week assessment periods are weeks 35 through 38 and weeks 61 through 64.
 
Compliance with treatment and data entry will be facilitated by email and text message reminders and prompts. Each subject will be compensated for participation and data collection based on a pre-defined schedule with a maximal milestone determined compensation of \$525 (Section 5.5).
 
ePRO symptom data and outcomes surveys will be collected according to a pre-defined schedule (Table 1).

Objectives:	
Primary Objective
 
The primary objective of this study is to demonstrate that in adults with Irritable Bowel Syndrome (IBS), an all-digital Gut-Directed Hypnotherapy (GDH) treatment program (Regulora) is superior in reducing abdominal pain intensity relative to an all-digital modified Jacobsonian Muscle Relaxation (MR) treatment program.

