3.3 Risk/Benefit Assessment

3.3.1 Known Potential Risks

Hypnotherapy is generally considered to be safe and low risk. Safety concerns have been proposed based on the observation that subjects with dissociative disorders (i.e., multiple

personality disorder) have an enhanced hypnotizability and under hypnosis may adopt an alternate identity or personality state (17-19). Elicitation of an alternate personality state and/or repressed memories, which are often past traumatic events, can be a painful experience for subjects. At the same time, it is important to note that hypnosis is used to treat dissociative disorder and the closely related syndrome of post-traumatic stress disorder (20). Therefore, the standard approach to minimizing the risk in hypnotherapy studies requires exclusion of subjects with these psychiatric conditions. In a review examining data from 7 hypnotherapy trials on ClinicalTrials.gov, it was found that studies that use these exclusion criteria had low rates of treatment-related adverse events (AEs) (<1% non-serious AEs) and no serious adverse events (SAEs) (20). Of the treatment-related AEs, there were 2 cases of disturbing images and thoughts and 2 cases of nightmares. A recent large European study confirmed these results: in 300 subjects allocated to therapist-administered GDH there were no SAEs or AEs that were deemed related to treatment (12).

It is also believed that the hypnotizability of subjects with active co-morbid psychiatric/mood disorders may be diminished and available literature indicates that subjects with these conditions should generally be excluded from clinical trials.

Finally, there are anecdotal therapist reports of mild headache, lightheadedness and disorientation that tend to spontaneously resolve within a short period after post-hypnotherapy arousal. As a precaution, subjects will be told to find a quiet place to view the treatment sessions and not to undergo treatment while driving or performing other tasks.

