4.2.2 Secondary Endpoints

The secondary efficacy endpoints of this study include:

- Overall mean change from Phase 1 to Phase 3 and Phase 1 to Phase 4 (LTE) in:

- Abdominal pain intensity
- Abdominal pain frequency
- Irritable Bowel Syndrome-Quality of Life questionnaire (IBS-QOL)
- Daily stool consistency (IBS-D and IBS-M)
- Daily stool frequency (IBS-C)
- Workplace Productivity and Activity Impairment questionnaire (WPAI)
- 12-week trends during Phase 2 in:
 - Abdominal pain intensity
 - Abdominal pain frequency
 - Daily stool consistency
 - Daily stool frequency

Safety and tolerability will be evaluated by comparing adverse events in the treatment arm versus comparator arm.

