8.4.8 PHQ-4

The PHQ-4 is a simple 4 item measure of anxiety (2 items) and depression (2 items) (24). Each item is scored on a 4-point (0-3) NRS and the items are summed to give a total score ranging from 0-12. The total score provides an assessment of psychological distress. The 2-item anxiety and depression scales can also be scored and scores of 3 or greater are considered positive for screening purposes. The PHQ-4 will be measured at baseline in the Phase 1 pre-treatment run-in period, week 16 (Phase 3), week 38, and at week 64 in the LTE.

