8.6 Adverse Events and Serious Adverse Events

8.6.1 Definition of Adverse Events

Adverse event¹ means any untoward medical occurrence, unintended disease or injury, or untoward clinical signs in subjects, whether or not related to the investigational medical device (21 CFR 312.32 (a)).

In the context of the investigational device, an AE constitutes:

- any unintentional, unfavorable clinical sign or symptom, including complications of IBS (but not IBS itself).
- any new illness or disease or the deterioration of existing IBS

¹ ISO14155 and 21 CFR 812

- any clinically significant deterioration in any clinical assessment or outcome measure
- Any adverse event resulting from insufficiencies or inadequacies in the instructions for use, the deployment, the installation, the operation or any malfunction of the investigational medical device. This includes any event that is a result of a use error or intentional abnormal use of the investigational medical device

Pre-existing conditions (unless worsened significantly during treatment) or routine diagnostic and therapeutic procedures normally administered in the treatment of IBS do not constitute AEs. AEs will be collected from the time a subject signs the informed consent until study withdrawal, screen failure, or study completion.

If the subject experiences a worsening or complication of an AE after ongoing treatment, the worsening or complication should be recorded as a new AE. Investigators should ensure that the AE term recorded captures the change in the condition (e.g., “worsening of...”).

In this study, it is possible that some subjects may experience a worsening of IBS symptoms. As the primary endpoint of this study, worsening of IBS symptoms is captured as part of the efficacy parameter. Worsening of IBS symptoms should not be considered an AE unless the worsening of the symptoms is associated with a cause other than the subject’s IBS.

All AEs that occur in study subjects during the AE reporting period specified in the protocol must be reported, WHETHER OR NOT THE EVENT IS CONSIDERED RELATED TO THE STUDY TREATMENT.

NONSERIOUS AEs are to be documented on the AE CRFs.

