8.6.5 Adverse Event and Serious Adverse Event Reporting

The occurrence of AEs, SAEs, and Protocol Deviations (PDs) shall be reported through a unidirectional, HIPAA-compliant, web-based communication channel. Event reports may be initiated at any time by the subject or the investigator. All logging of event reports shall be retained for the duration of the study to provide proper documentation in accordance with FDA and ICH GCP requirements. The adverse event will be triaged based on subject content and urgency.

In the event of an AE, SAE, or PD, the message will be immediately sent to the Curebase team for determination of severity and relatedness to the investigational treatment. The study team will

collect information from the subject as necessary and create a final event report for logging within a specified timeframe. Reports containing AEs will be processed and documented.

Reports containing SAEs shall be completed and filed per regulatory requirements. The information in a SAE report should be completed as fully as possible and contain at a minimum:

- Subject ID number
- Start date of the event
- Description of the event
- Study physician's name
- Investigator causality assessment
- Investigator seriousness assessment

If safety information not available at the time of the first report becomes available at a later date, the study team member should submit follow-up safety information to Curebase. All SAEs should be followed up until resolution or permanent outcome of the event. The timelines and procedure for follow-up reports are the same as those for the initial report. Detailed study reporting procedures shall be standardized as documented in a formal Safety Monitoring Plan.

9 Statistical Considerations

A Statistical Analysis Plan (SAP) will be prepared and finalized before unblinding of subjects' treatment assignment. This document will provide further details regarding the definition of analysis variables and analysis methodology to address all study objectives. A blinded data review will be conducted before unblinding of subject's treatment assignment. This review will assess the accuracy and completeness of the study database, subject evaluability, and appropriateness of the planned statistical methods.

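### No scheduled, solicited adverse-event question is specified after randomisation, which weakens the by-arm adverse-event comparison listed as a secondary safety endpoint

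*Combined protocol and SAP*

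**What the plan says.** The AE comparison is a listed endpoint. Section 4.2.2 states: "Safety and tolerability will be evaluated by comparing adverse events in the treatment arm versus comparator arm". The synopsis places it under secondary safety endpoints, and section 8.5 names AE reporting as the means of assessing safety. Section 9.4.5 plans counts and percentages by arm, with no test and no expected rate.

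On how an AE becomes known, section 8.6.4 says that it "may come to the attention of study personnel during study visits and interviews of a study subject presenting for medical care"; the same sentence adds review by a monitor. On conduct after randomisation, the synopsis says that "all subsequent data collection will be done without human intervention via the Curebase platform". Section 8.6.5 sets up a one-way web channel: "Event reports may be initiated at any time by the subject or the investigator". It refers to a Safety Monitoring Plan for detailed reporting procedures.

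Table 1 marks AE reports with an X in run-in, onboarding, treatment, run-out and both long-term extension periods.

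Section 8.6.3.5 lists the anticipated events: headache, drowsiness, fatigue, gastrointestinal discomfort, and muscle tightness or soreness. Section 3.3.1 reports from a review of seven hypnotherapy trials that "there were 2 cases of disturbing images and thoughts and 2 cases of nightmares".

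**The concern.** Section 8.6.4 reads as if written for a trial with clinic visits, and this trial has none after randomisation. If no one asks subjects at set times whether anything has happened, the count depends on who chooses to report. Most of the anticipated events are mild and short-lived, the kind that people often do not volunteer.

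This is a pivotal trial, and section 5.1 makes safety part of its hypothesis. A low AE count from unsolicited reports cannot separate few events from few reports. A difference between arms could likewise reflect a difference in reporting.

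**Working it through.** **Step 1: what is scheduled after Day 0.** These passages, set side by side, cover the routes to AE capture.

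- *Visits.* The post-Day 0 columns of Table 1 are periods, not visits. The last scheduled human contact is the onboarding call on the day of randomisation (section 2.3).
- *Instruments.* Sections 8.4.1 to 8.4.10 and 8.5.2 cover pain, stool, IBS-QOL, WPAI, TIS, PHQ-4, adequate relief, satisfaction and blinding. None asks about AEs. Section 8.5.1 collects medications and therapies with their indication, which may hint at an event but is not an AE query.
- *The AE row of Table 1.* Other post-randomisation rows say daily, once at a named week, or continuous import. The AE row has only an X.
- *Reports.* Section 8.6.5 lets the subject or investigator start a report at any time. The investigator has no scheduled contact at which to learn of an event. A monitor can review only what has been recorded.
- *Relatedness.* Section 8.6.3.4 requires a clinician who carries out an examination and evaluation. No examination is scheduled after baseline, and section 8.6.5 sends each report to the Curebase team to determine relatedness.

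So the protocol describes no solicited, scheduled AE query after randomisation. Whether the X in Table 1 stands for one is not stated.

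**Step 2: what incomplete capture does.** The plan gives no AE rate, test or power for safety, so it has no figure to reproduce. Let *p* be the true proportion of subjects with an AE in an arm and *c* the share of those recorded. The observed proportion is *p* × *c*.

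- Equal capture in both arms: observed difference = *c* × (p_GDH − p_MR). The ratio is unchanged and the absolute excess shrinks.
- Equal true rates, unequal capture: observed difference = *p* × (c_GDH − c_MR), a difference that is not real.

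**Step 3: range on assumed inputs.** Subjects per arm: 380 / 2 = 190. The documents give no value of *c*; I take 25% to 50%. For *p*, the nearest figure is the rate below 1% for treatment-related non-serious AEs in section 3.3.1. I take 1% as the low case, and 20% for any AE as an assumed high case.

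- *p* = 1%: 190 × 0.01 = 1.9 subjects. Recorded: 1.9 × 0.50 = 0.95, or 1.9 × 0.25 = 0.475. Missed: 0.95 to 1.4 per arm.
- *p* = 20%: 190 × 0.20 = 38 subjects. Recorded: 38 × 0.50 = 19, or 38 × 0.25 = 9.5. Missed: 19 to 28.5 per arm.
- *p* = 20% in both arms with capture of 50% against 25%: 10% against 5% observed. With 60% against 40%: 12% against 8%. Either arm could be the one that looks worse.

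The spread of these results shows that the loss cannot be sized from the documents.

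**The case against.** The case on the other side is substantial. The AE row of Table 1 may stand for a prompted form. The Safety Monitoring Plan may describe one, and the consent pages, which may carry AE instructions to subjects, were removed from the text. Monitor review is a named source. Subjects whose IBS symptoms change may call Curebase or seek the study physician's advice (section 3.3.3), and the app's help section gives contacts for problems with treatment (section 7.1.1). Missed data prompt email and phone contact (section 8.3), and withdrawal reasons must be sought (section 8.1). Known event rates are low, and the AE analysis is descriptive. All of this stands, but none of these described routes is a scheduled AE question, and how a listed endpoint is measured belongs in the protocol.

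A reader might infer more than the documents support:

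- *That spontaneous web reports are the sole source of AEs.* The routes above contradict this.
- *That the weeks without a scheduled assessment measure the problem.* Weeks 17-34 and 39-60 are 18 + 22 = 40 of 64 weeks, but all follow the 12-week treatment period, while most anticipated events are tied to sessions. A question on the existing surveys adds no contact in those weeks.
- *That the arms are primed to report differently.* Appendix F mentions not being fully alert and Appendix G muscle discomfort, but section 3.3.3 lists both drowsiness and muscle aches as study risks. No effect on reporting is shown.
- *That PHQ-4 needs a week 8 assessment or an automatic flag.* Section 8.6.1 does count "any clinically significant deterioration in any clinical assessment or outcome measure" as an AE. But PHQ-4 is exploratory here (sections 4.2.3 and 9.4.4), and section 8.4.8 says only that subscale "scores of 3 or greater are considered positive for screening purposes". Crossing that cut-off can be a one-point change, which the protocol does not call clinically significant deterioration.

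**Conclusion.** The concern holds as a gap in specification. After randomisation the protocol describes no solicited, scheduled AE query, section 8.6.4 relies on visits that the schedule does not contain, and the AE row in Table 1 is undefined. If the plan is followed as written, under-recording of mild events is likely and the by-arm AE comparison is weakened.

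The size is unknown: about one subject per arm in the low case and up to about 28 in the high case, on assumed rates and capture. No difference between arms has been shown. The conclusion rests on the protocol text alone, so a Safety Monitoring Plan that already contains an AE question would reduce the point to aligning the documents. The primary endpoint and its power do not depend on AE capture. The change should be made, but the main result does not depend on it.

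**What to change.** 1. Define the AE row of Table 1 as one open question, worded identically in both arms, for example *Have you had any new or worsened health problem since the last survey?* Add it to the Curebase surveys already scheduled at weeks 8, 16, 38 and 64.
2. In section 9.4.5, tabulate solicited and spontaneous AEs separately by arm.
3. Rewrite section 8.6.4 to describe the routes that exist in a remote trial, and state what the Safety Monitoring Plan adds.
4. Reconcile section 8.6.3.4 (a clinician's examination) with the absence of any scheduled examination and with the role that section 8.6.5 gives to the Curebase team.

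The cost is one item on four existing surveys and two extra tables. Reported AE percentages will rise, and there will be more mild-event queries to process. Recall is a limit: the intervals between the later surveys are 16 − 8 = 8, 38 − 16 = 22 and 64 − 38 = 26 weeks, so the question will work best for the treatment period and less well in the extension.
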